Box plots of local laboratory values will be generated for baseline values and for values measured during the study by treatment arm and visit. Each box plot will show the first quartile, the median, and the third quartile. Outliers will also be plotted. If appropriate, horizontal lines representing boundaries for abnormal values will be plotted. The number (percentage) of participants with local laboratory values recorded as meeting Grade 3 AE criteria or above as specified in the DAIDS AE Grading Table will be tabulated by treatment arm. Reportable clinical laboratory abnormalities without an associated clinical diagnosis will also be included in the tabulation of AEs described above.

- **Efficacy Reports**

The efficacy reports will be shared with the DSMB committee when required as per the analysis methodology mentioned in section 7.2.2 and 7.3.1 of the SAP ()above.

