APPENDIX E – Adverse Events of Special Interest

Adverse events of special interest (AESI) have been determined for CAB based on pre-clinical and clinical experience, along with information for the integrase inhibitor class of HIV medications safety profile. These are adverse events for which more detailed summaries of event characteristics are of interest. Details of the analyses of AESI are contained in Section **Error! Reference source not found.** based on the current MedDRA version used for the study, v23.1.

The identification and classification of AESI will have occurred as a clinical review of preferred terms for adverse events, lab data, ECG and vital signs prior to the unblinding of the studies. (see Appendix E Section 1).

Table 1 shows the adverse events of special interest identified and reasons for including.

Table 1 Adverse Events of Special Interest

AESI	Product Implicated	Reason for Including as AESI
Hepatic Safety Profile: Assessment of risk of hepatotoxicity	CAB	Clinical, Class, Regulatory Interest,
Hypersensitivity Reactions (HSR)	CAB	Class, Regulatory Interest,
Rash	CAB	Class, Regulatory Interest
Neuropsychiatric Events 
 • Suicidal Ideation/Behaviour • Depression • Bipolar Disorder • Psychosis • Mood Disorders • Anxiety • Sleep Disorders 	CAB	Clinical, Class, Regulatory Interest,
Injection Site Reactions (ISR)	CAB	Clinical, Regulatory Interest
Seizures and Seizure-like events	CAB	Clinical, Regulatory Interest
Weight Gain	CAB	Clinical, Class, Regulatory Interest
Rhabdomyolysis	CAB	Clinical, Class, Regulatory Interest
Pancreatitis	CAB	Clinical, Therapeutic Area, Regulatory Interest

Impact on Creatinine	CAB	Regulatory Interest, Therapeutic Area
Safety in Pregnancy (Does not apply to HPTN083)	CAB	Regulatory Interest, Class
Hyperglycaemia/new onset diabetes mellitus	CAB	Observation from 083, Class

Common ISR adverse events are defined by MedDRA preferred terms including injection site pain, injection site induration, injection site nodules and preferred terms of any other ISR with $\geq 5\%$ participants in either treatment arm. ISRs are summarized and listed regardless of IP relationship.

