Although not pre-specified as an AESI, further analysis of pyrexia and related terms (Pyrexia Plus), sciatica and specific musculoskeletal related terms, and pancreatitis and related terms (Pancreatitis Plus) will be conducted, based on regulatory interest in the treatment indication, in order to characterise these phenomena in the PrEP population.

The following preferred terms have been identified for these areas of interest:

Pyrexia Plus includes PT: (Chills – 10008531, Feeling of Body Temperature Change - 10061458, Feeling Hot - 10016334, Body Temperature Increased - 10005911, Pyrexia - 10037660, Influenza Like Illness - 10022004, Fever – 10016558).

Sciatica PT: (Sciatica - 10039674) and specific Musculoskeletal includes PT: (Back pain – 10003988, Myalgia – 10028411, Pain in extremity – 10033425, Musculoskeletal pain - 10028391).

Pancreatitis Plus includes PT: (Pancreatitis - 10033645, Pancreatic enzymes increased - 10061900, Abdominal pain - 10000081, Abdominal pain upper - 10000087, Abdominal discomfort - 10000059, Nausea - 10028813). When looking at Pancreatitis Plus events after elevated lipase, the elevated lipase is defined as lipase above the upper limit of normal (ULN).

Section 1: AE Preferred Term for AESI identification (based on MedDRA v23.1)

Hepatotoxicity (Hepatic failure, fibrosis and cirrhosis and other liver damage-related conditions)

PT	PT Code
Acquired hepatocerebral degeneration	10080860
Acute hepatic failure	10000804
Acute on chronic liver failure	10077305
Acute yellow liver atrophy	10070815
Ascites	10003445
Asterixis	10003547
Bacterascites	10068547
Biliary cirrhosis	10004659
Biliary fibrosis	10004664
Cardiohepatic syndrome	10082480

Cholestatic liver injury	10067969
Chronic hepatic failure	10057573
Coma hepatic	10010075
Cryptogenic cirrhosis	10063075
Diabetic hepatopathy	10071265
Drug-induced liver injury	10072268
Duodenal varices	10051010
Flood syndrome	10084797
Gallbladder varices	10072319
Gastric variceal injection	10076237
Gastric variceal ligation	10076238
Gastric varices	10051012
Gastric varices haemorrhage	10057572
Gastrooesophageal variceal haemorrhage prophylaxis	10066597
Hepatectomy	10061997
Hepatic atrophy	10019637
Hepatic calcification	10065274
Hepatic cirrhosis	10019641
Hepatic encephalopathy	10019660
Hepatic encephalopathy prophylaxis	10066599
Hepatic failure	10019663
Hepatic fibrosis	10019668
Hepatic hydrothorax	10067365
Hepatic infiltration eosinophilic	10064668
Hepatic lesion	10061998

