PT	PT Code
Acquired lipoatrophic diabetes	10073667
Blood 1,5-anhydroglucitol decreased	10065367
Blood glucose increased	10005557
Diabetes complicating pregnancy	10012596
Diabetes mellitus	10012601
Diabetes mellitus inadequate control	10012607
Diabetes with hyperosmolarity	10012631
Diabetic arteritis	10077357
Diabetic coma	10012650
Diabetic coronary microangiopathy	10080788
Diabetic hepatopathy	10071265
Diabetic hyperglycaemic coma	10012668
Diabetic hyperosmolar coma	10012669
Diabetic ketoacidosis	10012671
Diabetic ketoacidotic hyperglycaemic coma	10012672
Diabetic ketosis	10012673

Diabetic metabolic decompensation	10074309
Diabetic wound	10081558
Euglycaemic diabetic ketoacidosis	10080061
Fructosamine increased	10017395
Fulminant type 1 diabetes mellitus	10072628
Gestational diabetes	10018209
Glucose tolerance impaired	10018429
Glucose tolerance impaired in pregnancy	10018430
Glucose urine present	10018478
Glycated albumin increased	10082836
Glycosuria	10018473
Glycosuria during pregnancy	10018475
Glycosylated haemoglobin abnormal	10018481
Glycosylated haemoglobin increased	10018484
Hyperglycaemia	10020635
Hyperglycaemic hyperosmolar nonketotic syndrome	10063554
Hyperglycaemic seizure	10071394
Hyperglycaemic unconsciousness	10071286
Impaired fasting glucose	10056997
Insulin resistance	10022489
Insulin resistant diabetes	10022491
Insulin-requiring type 2 diabetes mellitus	10053247
Ketoacidosis	10023379
Ketonuria	10023388
Ketosis	10023391
Ketosis-prone diabetes mellitus	10023392
Latent autoimmune diabetes in adults	10066389
Monogenic diabetes	10075980
Neonatal diabetes mellitus	10028933
New onset diabetes after transplantation	10082630

Pancreatogenous diabetes	10033660
Steroid diabetes	10081755
Type 1 diabetes mellitus	10067584
Type 2 diabetes mellitus	10067585
Type 3 diabetes mellitus	10072659
Urine ketone body present	10057597

Hypersensitivity Reactions Drug reaction with eosinophilia and systemic symptoms syndrome

PT	PT Code
Drug reaction with eosinophilia and systemic symptoms	10073508
Pseudolymphoma	10037127
Granulomatous T-cell pseudolymphoma	10084214
Drug hypersensitivity	10013700
Hypersensitivity	10020751
Type IV Hypersensitivity reaction	10053613
Eosinophilia	10014950
Eye swelling	10015967
Eyelid oedema	10015993
Lip swelling	10024570
Angioedema	10002424
Circumoral oedema	10052250
Face oedema	10016029
Idiopathic angioedema	10073257
Lip oedema	10024558
Mouth swelling	10075203
Oedema mouth	10030110
Periorbital oedema	10034545

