Depressed level of consciousness	10012373
Consciousness fluctuating	10050093

Weight Gain

PT	PT Code
Abdominal fat apron	10077983
Overweight	10033307
Abnormal weight gain	10000188
Central obesity	10065941
Obesity	10029883
Weight abnormal	10056814
Weight increased	10047899
Waist circumference increased	10064863
Body mass index abnormal	10074506
Body mass index increased	10005897
Fat tissue increased	10016251
Sarcopenic obesity	10083992

Rhabdomyolysis

PT	PT Code
Muscle necrosis	10028320
Myoglobin blood increased	10028625
Myoglobin blood present	10059888
Myoglobin urine present	10028631
Myoglobinaemia	10058735
Myoglobinuria	10028629
Myopathy	10028641
Myopathy toxic	10028648
Necrotising myositis	10074769
Rhabdomyolysis	10039020
Thyrotoxic myopathy	10081524
Myalgia	10028411
Myositis	10028653

Pancreatitis

PT	PT Code
Cullen's sign	10059029
Grey Turner's sign	10075426
Haemorrhagic necrotic pancreatitis	10076058
Hereditary pancreatitis	10056976
Immune-mediated pancreatitis	10083072
Ischaemic pancreatitis	10066127
Oedematous pancreatitis	10052400
Pancreatic abscess	10048984
Pancreatic cyst drainage	10082531

Pancreatic haemorrhage	10033625
Pancreatic necrosis	10058096
Pancreatic phlegmon	10056975
Pancreatic pseudoaneurysm	10081762
Pancreatic pseudocyst	10033635
Pancreatic pseudocyst drainage	10033636
Pancreatic pseudocyst haemorrhage	10083813
Pancreatic pseudocyst rupture	10083811
Pancreatitis	10033645
Pancreatitis acute	10033647
Pancreatitis haemorrhagic	10033650
Pancreatitis necrotising	10033654
Pancreatitis relapsing	10033657
Pancreatorenal syndrome	10056277
Subacute pancreatitis	10084554

Impact on Creatinine

PT	PT Code
Acute kidney injury	10069339
Acute phosphate nephropathy	10069688
Anuria	10002847
Azotaemia	10003885
Continuous haemodiafiltration	10066338
Dialysis	10061105
Foetal renal impairment	10078987
Haemodialysis	10018875
Haemofiltration	10053090

Neonatal anuria	10049778
Nephropathy toxic	10029155
Oliguria	10030302
Peritoneal dialysis	10034660
Prerenal failure	10072370
Renal failure	10038435
Renal failure neonatal	10038447
Renal impairment	10062237
Renal impairment neonatal	10049776
Subacute kidney injury	10081980
Atypical haemolytic uraemic syndrome	10079840
Cardiorenal syndrome	10068230
Chronic kidney disease	10064848
Crush syndrome	10050702
Diabetic end stage renal disease	10012660
End stage renal disease	10077512
Foetal renal impairment	10078987
Haemolytic uraemic syndrome	10018932
Hepatorenal failure	10019845
Hepatorenal syndrome	10019846

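### SAP Appendix E: the AESI named for creatinine has no creatinine, creatinine-clearance or GFR term in its list, and the SAP does not say how laboratory data enter the AESI summaries

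*SAP*

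**What the plan says.** Appendix E, Table 1 lists the AESIs, among them "Impact on Creatinine", "Hepatic Safety Profile: Assessment of risk of hepatotoxicity" and rhabdomyolysis. Section 1 of the appendix gives the preferred terms for each.

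- The creatinine list opens with "Acute kidney injury" and continues with renal failure, dialysis and related conditions and syndromes.
- The hepatic AESI has two lists. The first is headed "Hepatotoxicity (Hepatic failure, fibrosis and cirrhosis and other liver damage-related conditions" and the second covers non-infectious hepatitis.
- The rhabdomyolysis list mixes muscle diagnoses with myoglobin findings such as "Myoglobin blood increased".

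On method, Appendix E says: "The identification and classification of AESI will have occurred as a clinical review of preferred terms for adverse events, lab data, ECG and vital signs". It places that review before unblinding and points to Section 1. The reference to the section holding the AESI analyses is an unresolved field error.

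Laboratory data are also handled outside the AESIs. Section 7.3.5 reports creatinine, CPK, AST, ALT, total bilirubin and alkaline phosphatase by grade. Section 9.1 says of the monitoring reports: "Reportable clinical laboratory abnormalities without an associated clinical diagnosis will also be included in the tabulation of AEs described above".

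**The concern.** An AESI defined by a preferred-term list can only count events coded to a term on that list. A list headed for creatinine that has no creatinine term does not measure what its heading says. In this trial creatinine is measured and graded, and Section 9.1 expects laboratory abnormalities without a diagnosis to be handled as adverse events. An event coded only to raised creatinine is therefore a foreseeable case, and the list would miss it.

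Appendix E describes AESIs as events for which fuller summaries of event characteristics are wanted. Those fuller summaries are what is at stake. A renal AESI table with few or no events could be read as covering creatinine changes when it does not.

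**Working it through.** The SAP gives no figure to reproduce here. The check is a count of terms and a comparison of sections.

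**Step 1. Creatinine list (Appendix E, Section 1).** There are 44 rows. Eight terms are entered twice: foetal renal impairment, neonatal anuria, oliguria, prerenal failure, renal failure, renal failure neonatal, renal impairment and renal impairment neonatal. Distinct terms: 44 − 8 = 36. Terms naming creatinine, clearance or GFR: 0 of 36. The nearest biochemical term is azotaemia.

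**Step 2. Could the terms have been lost in the document?** Section 10.2.1 says the AESI appendix was truncated in Version 3.0 and has been corrected in Version 4.0. The list is two alphabetical blocks, and in the first a term beginning with Blood would fall between azotaemia and continuous haemodiafiltration, and one beginning with Creatinine between continuous haemodiafiltration and dialysis. Those three rows run on without a break. Nothing points to a lost row.

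**Step 3. Hepatic lists.** There are 107 rows, with three terms entered twice (hepatitis fulminant, non-alcoholic steatohepatitis, steatohepatitis). Distinct terms: 107 − 3 = 104. Terms naming an aminotransferase, liver enzyme, bilirubin, alkaline phosphatase or liver function test: 0 of 104.

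**Step 4. Rhabdomyolysis list.** There are 13 terms and none names CPK. Three are laboratory findings for myoglobin in blood or urine. Myalgia is also listed.

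**Step 5. Does the appendix exclude laboratory terms in general?** No. The hyperglycaemia list has "Blood glucose increased" and a raised fructosamine term. The weight list has weight-increase and BMI-increase terms. The rhabdomyolysis list has the myoglobin terms. Pancreatitis Plus, in Appendix E Section 3, has a raised pancreatic-enzyme term. A diagnosis-only rule therefore does not explain the creatinine list.

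**Step 6. Does another rule bring creatinine in?** Where Appendix E wants a source other than the term list, it says so: CRF terms for injection site reactions, terms co-reported with pregnancy exposures for pregnancy safety, and lipase above the upper limit of normal when Pancreatitis Plus events after raised lipase are examined. It gives no such rule for creatinine, liver enzymes or CPK. The sentence quoted from Appendix E does name laboratory data, but it does not say how a laboratory finding becomes an AESI event in an output.

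**Step 7. Where would an isolated creatinine event still appear?**

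| SAP section | What it reports |
|---|---|
| 7.3.2 | Primary safety comparison on all adverse events of maximum grade 2 or higher, not on AESI lists |
| 7.3.5 | Creatinine and the other analytes by grade, with the proportion at grade 2 or above, and values by arm |
| 9.1 | Number and percentage with laboratory values at grade 3 or above, by arm, in monitoring reports |
| 9.2 | All adverse events by arm, preferred term and severity; laboratory values and changes by visit |

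The event is therefore visible in the study report. It is missing only from the AESI summary, and only if that summary selects on Section 1 terms.

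**The case against.** The strongest reply is that the plan already makes laboratory data an input to AESI identification, so nothing is excluded. Part of this stands: the SAP never says that an event outside the Section 1 lists is not an AESI event. But the same sentence points to Section 1, and the natural reading is that the lists are the product of that review. With the reference to the AESI analyses broken, a programmer has only the lists to work from. The position is unclear, and the likeliest reading is selection on the listed terms.

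A second reply is that keeping AESI lists to diagnoses is a legitimate choice that protects specificity. This has force for the hepatic AESI, whose list headings declare a scope of liver damage and hepatitis. It also has some force for rhabdomyolysis, where the list already reaches beyond diagnoses through myoglobin and myalgia. It does not rescue a list named for a laboratory analyte, in an appendix where other lists carry laboratory terms.

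A third reply is that the Section 9.1 sentence concerns monitoring reports and does not say how laboratory events are coded. That is correct. That such events receive laboratory preferred terms is an inference. It is supported by MedDRA coding of all adverse events in Section 9.2 and by the laboratory adverse event listed among the discontinuation reasons in Appendix C.

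A reader might go further and infer that the arm comparison for renal, hepatic and muscle risk would rest on a few clinical diagnoses and look falsely clean. The documents do not support this. The primary safety comparison does not use the AESI lists, and the general adverse-event tables and graded laboratory results are unaffected. Nor do they give any basis for a percentage of creatinine events missed.

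**Conclusion.** The point holds for the creatinine AESI: 0 of 36 distinct terms name creatinine, clearance or GFR. An adverse event coded only to raised creatinine would then not be counted under that AESI. This rests on two assumptions: that the summaries select on Section 1 terms, and that laboratory-only events are coded to laboratory terms. The effect is limited to the descriptive AESI output and does not touch the primary efficacy analysis, the primary safety comparison or the graded laboratory reporting.

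For the hepatic lists (0 of 104 distinct terms) and the rhabdomyolysis list (0 of 13 naming CPK) the same gap exists. There it is a matter for clarification, since a narrower scope is defensible if it is stated.

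**What to change.** 1. Add to the creatinine list the MedDRA v23.1 preferred terms for raised or abnormal creatinine and for reduced creatinine clearance or GFR. Show laboratory-only events on a separate line.
2. For the hepatic and rhabdomyolysis AESIs, either add liver-enzyme, bilirubin and CPK terms on the same separate line, or state that these risks are assessed from the graded laboratory data of Section 7.3.5.
3. Repair the broken reference in Appendix E, and state how the review of laboratory data feeds the AESI summaries.

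The cost is appendix wording and an updated lookup table, with no new data collection and no effect on type I error. The downside of adding terms is higher and less specific AESI counts; the separate line keeps the clinical diagnoses visible.
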